
1. Participants will complete Virtual Visit 2 between 1 and 21 days after completing In-Person Lab Visit 1. Virtual Visits 2-5 will ideally be conducted four days in a row to reduce online task fatigue. However, visits may be scheduled up to 7 days apart.

The following assessments will be administered as an interview and entered into REDCap by the interviewer:

1. Timeline Follow Back (TLFB) Questionnaire, which will assess tobacco and nicotine product use since their last virtual visit.

The following surveys will be self-administered using REDCap:

1. Minnesota Nicotine Withdrawal Scale
2. Questionnaire of Smoking Urges-Brief – Usual Brand Cigarette

Participants will complete the ETM task on the computer. If the participant needs assistance with navigating the online marketplace the research staff may screen share and allow the participant to verbally select the items that they would like to purchase. The products available on the ETM include:

- Menthol and non-menthol cigarettes (matched to the participant's preferred brand)
- Fruit, dessert, mint, menthol and tobacco e-liquids (e.g., Suorin iShare)
- Mint, fruit, and cinnamon nicotine gum (e.g., Nicorette).

Participants will undergo one of four marketplace conditions during Virtual Visits 2-5, with the order of administration randomized across participants.

- Marketplace Condition 1 includes only tobacco e-liquids.
- Marketplace Condition 2 includes menthol and tobacco e-liquids.
- Marketplace Condition 3 includes mint menthol, and tobacco e-liquids.
- Marketplace Condition 4 includes fruit, dessert, mint, menthol, and tobacco e-liquids.

Staff will instruct participants to complete the ETM task as if they are purchasing the products from a retailer, and that one iteration of the task will be randomly selected and will determine which products they will use during the field assessment. In reality, we will randomly assign which condition is used 1, 2, 3, or 4 but will assign products based on when menthol cigarettes were not available each to simulate a menthol cigarette ban.

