For each marketplace condition, participants will complete 10 iterations of the ETM task in ascending order. The prices for menthol cigarettes on the ETM will be set at: \$0.12, \$0.25, \$0.50, \$1.00, \$2.00, \$4.00, \$8.00, and \$16.00 and \$32.00 per cigarette. During one task iteration, menthol cigarettes will be eliminated from the marketplace to simulate a menthol cigarette ban. The costs for the other products will reflect average prices in NC and will not change during the task. For each task iteration, participants will receive individually-tailored account balances approximately equal to the money they would spend on cigarettes for seven days. They can

purchase as many or few products as their account balance allows. Participants are not required to buy products from the ETM or can buy nicotine gum if they prefer to abstain. If they do not buy products from the ETM and do not use tobacco products during the field assessment (biochemically-verified), then they will receive their ETM account balance at Virtual Visit 6. This payment is delayed to reduce the likelihood that they will use this money to buy their preferred brand menthol cigarettes, thus decreasing the validity of the ETM task.

Participants will be instructed to use only the products purchased from the ETM during the subsequent 7-day period after Virtual Visit 5 and told that we will assess adherence by self-report, product accountability, and biochemical verification. The field assessment validates the ETM task by having participants use the products in the real world, simulating the different regulatory environments. Actual product use enables us to measure their subjective experiences such as withdrawal, craving, or product satisfaction as well as assess changes in carbon monoxide exposure, a biomarker of harm, when using products other than menthol cigarettes. We will conduct between-subjects analyses comparing these secondary outcomes by marketplace condition.

In-Person Lab Visit 2

In-Person Lab Visit 2 will be completed up to 48 hours after completing Virtual Visit 5. Participants will complete the COVID screener within 24 hours of their Lab visit via email or phone. Research staff will wear personal protective equipment during the visit including face masks and gloves. The participants will be required to wear facemasks when interacting with the staff. Temperature checks will be conducted immediately upon arrival using a thermal heat scanner.

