Participants will provide CO readings be at least 6-feet away from other people, including the research staff, while they have their masks off.

Participants will be given the products they purchased during the ETM task and will be instructed to only use these products for the next seven days. They will also be given a urine collection cup and instructions for sample collection.

Virtual Visit 6

Participants will complete Virtual Session 6 seven days after completing In-Person Lab Visit 2. They will bring a first morning void urine sample, which will be banked for future biomarker analysis (e.g., total nicotine equivalents).

The following baseline assessments will be administered as an interview and entered into REDCap by the interviewer:

1. Timeline Follow Back (TLFB) Questionnaire which will assess past tobacco and nicotine product use since Virtual Visit 5.

The following surveys will be self-administered using REDCap:

1. Tobacco Policy Questionnaire
2. Minnesota Nicotine Withdrawal Scale

3. Questionnaire of Smoking Urges-Brief – Usual Brand Cigarette
4. Product Evaluation Scale
5. Perceived Health Risks Scale
6. Tobacco Product Interest Scale

Participants will complete the ETM task under the same marketplace condition from which they received their field assessment products. Exploratory pre-post field assessment analyses will examine how actual use of the products affects subsequent purchasing of those products.

Research staff will conduct in-depth interviews with the participants to assess the following constructions: 1) decision-making during the ETM task; 2) use of alternative products during the field assessment; 3) product risk perceptions and; 4) opinions regarding possible tobacco control policies.

In-Person Lab Visit 3

In-Person Lab Visit 3 will be completed up to 48 hours after completing Virtual Visit 6. Participants will complete the COVID screener within 24 hours of their Lab visit via email or phone. Research staff will wear personal protective equipment during the visit including face masks and gloves. The participants will be required to wear facemasks when interacting with the staff. Temperature checks will be conducted immediately upon arrival using a thermal heat scanner. Participants will bring a first void urine sample and all of their used/unused products.

Participants will provide CO readings at least 6-feet away from other people, including the research staff, while they have their masks off.

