All participants will be emailed a cessation manual and local smoking cessation resources.

Product adherence

To verify self-reported tobacco use, all used and unused products will be collected and counted at In-Person Lab Visit 3. Discrepancies between consumption stated on the TLFB versus consumption based on the products returned will be addressed. Non-adherence (i.e., using products not purchased from the ETM) will be assessed via the TLFB and qualitative interview with the importance of honest self-reporting emphasized. If participants report not using combusted tobacco, then CO readings < 6 ppm will verify their self-report.

Compensation

Participants will be paid \$155 for completing the study. They will earn \$30 for completing Virtual Visit 1, \$15 per visit for completing Virtual Visits 2-6 plus a \$50 bonus for completing the study.

Participants that do not meet enrollment criteria at Virtual 1 will earn \$20 for attending the visit. Participants that start but do not complete the study will receive payments for the virtual visits attended. They will not receive the \$50 completion bonus.

ANALYSIS PLAN

Primary Outcome

Protocol Version 10
5.13.22

- Total amount of non-menthol cigarettes purchased when menthol cigarettes are not available.

Secondary Outcomes

- Total amount of tobacco e-liquid purchased when menthol cigarettes are not available.
- Total amount of menthol e-liquid purchased when menthol cigarettes are not available.
- Total amount of mint e-liquid purchased when menthol cigarettes are not available.
- Total amount of dessert and fruit e-liquid purchased with menthol cigarettes are not available

Exploratory Outcomes

- Mean Perceived Health Risk Scale scores
- Mean Product Evaluation Scale scores
- Mean Minnesota Nicotine Withdrawal Scale scores
- Mean Questionnaire on Smoking Urges scores
- Mean Tobacco Product Interest scores
- Mean Tobacco Policy Questionnaire scores
- Total amount of non-menthol cigarettes purchased when menthol cigarettes are not available by race
- Total amount of tobacco e-liquid purchased when menthol cigarettes are not available by race.
- Total amount of menthol e-liquid purchased when menthol cigarettes are not available by race.
- Total amount of mint e-liquid purchased when menthol cigarettes are not available by race.
- Total amount of dessert/fruit e-liquid purchased when menthol cigarettes are not available by race.
- Themes emerging from the qualitative interviews

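### The product-only field week has two start points, and the buy-nothing payment falls due before the reading that could verify it

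*Combined protocol and SAP*

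**What the plan says.** **Start of the week.** Virtual Visits 2-5 states: "Participants will be instructed to use only the products purchased from the ETM during the subsequent 7-day period after Virtual Visit 5". The next section allows a gap before products are available: "In-Person Lab Visit 2 will be completed up to 48 hours after completing Virtual Visit 5". At that lab visit the products are handed over and participants "will be instructed to only use these products for the next seven days". Virtual Visit 6 is timed seven days after Lab Visit 2.

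**Records of use.** The TLFB at Virtual Visit 6 will "assess past tobacco and nicotine product use since Virtual Visit 5". This follows the convention of the preceding sessions, whose TLFB is one "which will assess tobacco and nicotine product use since their last virtual visit". Product adherence says that "all used and unused products will be collected and counted at In-Person Lab Visit 3", and "In-Person Lab Visit 3 will be completed up to 48 hours after completing Virtual Visit 6". It adds: "Discrepancies between consumption stated on the TLFB versus consumption based on the products returned will be addressed". No common interval is given. Non-adherence, meaning use of products not bought in the Experimental Tobacco Marketplace (ETM), is taken from the TLFB and the qualitative interview.

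**Payment.** Under Virtual Visits 2-5, a participant who buys nothing and uses no tobacco product in the field week, with biochemical verification, receives the account balance at Virtual Visit 6. No CO reading is listed at that visit, and its urine sample is banked for future work. The only verification rule, under Product adherence, is CO below 6 ppm for participants who report no combusted tobacco.

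**CO and field comparisons.** Virtual Visits 2-5 intends to assess changes in CO exposure and to compare field measures between marketplace conditions. CO is read at Lab Visits 1, 2 and 3. No section names the reference reading for that analysis.

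**The concern.** Virtual Visits 2-5 presents the field week as the validation of the ETM task, so adherence during it needs one definition. With two start points, a participant who smokes their usual brand after Virtual Visit 5 and before collecting products can be classed either way from the same TLFB entry.

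The payment rule asks staff to release money at a visit where no verifying result exists. The one stated rule also tests less than the payment condition requires: combusted tobacco rather than any tobacco product.

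Two smaller points follow from the same schedule. The TLFB and the product count stop at different times, so they can disagree when both are accurate. And an analysis of change in CO with two candidate baselines leaves the choice open until the data are in.

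**Working it through.** The plan gives no figure to reproduce here; the check is interval arithmetic on the visit schedule.

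**Timeline.** Let *a* be the lag from Virtual Visit 5 (VV5) to Lab Visit 2 (LV2), and *b* the lag from Virtual Visit 6 (VV6) to Lab Visit 3 (LV3). The plan allows 0 to 48 h for each. With VV5 at 0 h: LV2 = *a*, VV6 = *a* + 168, LV3 = *a* + 168 + *b*.

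**1. Start point.** The week from VV5 runs from 0 to 168 h; the week from hand-over runs from *a* to *a* + 168 h. They share 168 − *a* hours.

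| *a* | Shared hours | Share of week |
|---|---|---|
| 0 h | 168 | 100% |
| 24 h | 144 | 85.7% |
| 48 h | 120 | 71.4% |

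At *a* = 48 h the participant holds no study products for the first 48 h of the week that starts at VV5. The closing TLFB runs from 0 to *a* + 168 h, so it records use in that gap.

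**2. TLFB against product count.** The count covers *a* to *a* + 168 + *b*. Before LV2 no dispensed product exists, so the TLFB's extra *a* hours contain no study-product use. After VV6 the count can include *b* hours of study-product use that the TLFB does not. As a share of the count's calendar time this is *b*/(168 + *b*): 0% at 0 h, 24/192 = 12.5% at 24 h, 48/216 = 22.2% at 48 h. These are shares of time, not of consumption.

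**3. Payment against verification.**

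| Element | What is listed | When |
|---|---|---|
| Balance due | no tobacco product use, verified | VV6 |
| CO | none at VV6; next reading at LV3 | 0 to 48 h after VV6 |
| Urine | banked, no result planned | not available at VV6 |
| Stated rule | CO below 6 ppm, combusted tobacco only | needs the LV3 reading |

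CO at LV1 and LV2 precedes product use and cannot verify abstinence in the week after hand-over. Booking LV3 on the same day shortens the wait but leaves payment ahead of the result.

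**4. CO reference.** LV2 falls at *a*. That is the start of the hand-over week, but inside the week from VV5 whenever *a* > 0. The choice between LV1 and LV2 therefore depends on the start point. The adverse-event section refers to CO at the Screening/Baseline Visit, but only as a trigger for the adverse event form.

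**5. Precision of field comparisons.** Assumption: 80 completers split evenly over four conditions, 80/4 = 20 each (the allocation ratio is not stated). For a two-sample t-test at two-sided 0.05 with 80% power, the detectable difference is 0.909 SD. ANCOVA multiplies this by √(1 − r²). A change score multiplies it by √(2(1 − r)), taking equal SDs. The correlation r with the pre-field value is not given, so a range is shown.

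| r | Unadjusted | ANCOVA | Change score |
|---|---|---|---|
| 0.3 | 0.909 | 0.867 | 1.076 |
| 0.5 | 0.909 | 0.787 | 0.909 |
| 0.7 | 0.909 | 0.649 | 0.704 |

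With 15 against 25, the unadjusted value is 0.939; ANCOVA gives 0.896, 0.813 and 0.671.

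**The case against.** The best defence is that hand-over, the instruction given there and the timing of Virtual Visit 6 all point to Lab Visit 2, so the other sentence is loose wording. That is a plausible reading, and no adherence-based analysis set appears in the Analysis Plan. But the closing TLFB also starts at Virtual Visit 5, and non-adherence is scored from it, so the text does not settle which use counts.

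Several stronger readings are tempting, and the documents do not support them:

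- *The TLFB and the count each hold up to 22% that the other lacks, so up to that share of consumption is unreconciled.* No dispensed product can be used before Lab Visit 2, and field products come from the iteration without menthol cigarettes, while participants smoke menthol brands more than 80% of the time. Use in the first gap is mostly distinguishable from anything counted. Only the tail from Virtual Visit 6 to Lab Visit 3 distorts the comparison directly.
- *Nothing records use in that tail.* The count does, for study products, although it is undated.
- *The field comparisons are biased.* The field condition is randomly assigned, so unadjusted comparisons remain unbiased. The case for ANCOVA concerns precision alone, and the detectable differences rest on assumed allocation and correlations.
- *The CO check misses a known part of the week.* Any such figure needs an elimination half-life and a starting level that the documents do not give, so none is relied on here.

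It might also seem natural to score TLFB non-adherence only over the time both records share. That would be a mistake: if the week starts at Virtual Visit 5 and the lag is 48 h, it would drop 48 of the 168 instructed hours, which only the TLFB captures.

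**Conclusion.** Two conflicts in the text are established: the start of the product-only week, and payment due ahead of its verification. The second cannot be followed as written, whatever the lags. Two lesser gaps also stand: up to 48 h of study-product use that the count can include and the TLFB cannot, and the absence of a reference visit for change in CO.

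The consequence is minor. Aims 1 and 2 and the listed primary and secondary outcomes are ETM purchases and do not use the field-week windows. The field scales are listed as exploratory, and CO is not a listed outcome, although Virtual Visits 2-5 calls these measures secondary. With both lags at zero, the start-point and record mismatches vanish. The number of buy-nothing participants is not given and could be zero. The 48 h figures are maxima allowed by the schedule, not expected values. The change is worth making because most of it is wording.

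**What to change.** 1. **Start point.** Reconcile Virtual Visits 2-5, In-Person Lab Visit 2, Virtual Visit 6 and Product adherence to one field-week start. Score TLFB non-adherence over the whole of that reconciled week.
2. **Payment.** Reconcile the payment timing with the verification step and name the verifying test, matched to the condition of no tobacco product use, so that the balance is not due before the result.
3. **TLFB against count.** Hold Lab Visit 3 on the same day as Virtual Visit 6 where possible. Otherwise extend the TLFB to Lab Visit 3, and compare the two from hand-over to return.
4. **CO and scales.** Name the CO reference visit. As a precision gain only, analyse field CO and the scales with a matching pre-field measure by ANCOVA on field condition, race stratum and the latest pre-field value. For CO this is Lab Visit 2, or Lab Visit 1 if the reconciled week starts before Lab Visit 2. For withdrawal and urges it is Virtual Visit 5; for perceived risk, product interest and policy, Virtual Visit 1. The Product Evaluation Scale has no same-named pre-field measure and stays without baseline adjustment.

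**Cost.** Items 1 and 2 are protocol wording. Item 3 costs some scheduling flexibility, on a day that already holds surveys, an ETM task and an interview, or else a short added TLFB. Item 4 is analysis-plan wording on data already collected, at the price of a few model degrees of freedom.

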Aim 1: To determine how the availability of menthol e-liquids affects combusted tobacco purchasing in menthol cigarette smokers. *Hypothesis 1: Non-menthol cigarette purchasing will be greatest when only tobacco e-liquids are available, indicating that the availability of menthol e-liquids is important for encouraging menthol cigarette smokers to switch to potentially less harmful products.*

Aim 2: To establish if the availability of mint e-liquids is beneficial to menthol cigarette smokers. *Hypothesis 2: Non-menthol cigarette purchasing will not differ by more than 10% when only menthol e-liquids are available compared to when menthol and mint e-liquids are available, indicating that banning mint e-liquids would not discourage menthol cigarette smokers from switching to potentially less harmful products.*

Exploratory Aim: To evaluate the effect of menthol and mint e-liquid restrictions among black menthol cigarette smokers. The effects of the e-liquid marketplace manipulation will be replicated among black smokers.

METHODS AND MEASURES

Overall Study Design

We propose to conduct a within-subjects, multi-session virtual lab study and validation field assessment to determine how the availability of menthol and mint e-liquids affects product purchasing among menthol cigarette smokers. Adult daily menthol cigarette smokers (N=80) will be recruited for this study. After initial eligibility is assessed, participants will complete six virtual sessions (1 baseline, 4 experimental, and 1 follow-up), with three in-person components, and one field assessment to evaluate their tobacco use.

Design and Setting

Participants will be recruited from Winston-Salem, NC and the surrounding area using advertisements on public transit, community flyers, and social media. In a recent trial conducted in Winston-Salem enrolling daily cigarette smokers using similar recruitment methods (U54DA031659; PI: [name]), over 60% of participants were menthol cigarette smokers and 31% identified as black or African American. In-person lab visits to drop off biosamples and pickup study products will be conducted at the Wake Forest Tobacco Control Center of Excellence located in Biotech Place in the Innovation Quarter.

Subject Selection Criteria

We anticipate recruiting up to 100 participants to achieve 80 completers. Equal numbers of black and white participants will be enrolled.

Inclusion criteria:

1. 21+ years of age

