2. Minnesota Nicotine Withdrawal Scale a measure of nicotine withdrawal symptoms
3. Questionnaire of Smoking Urges-Brief – Usual Brand Cigarette, which measures the urge to smoke
4. Cigarette Evaluation Scale, which measures responses to cigarettes (e.g., reward, satisfaction)
5. Perceived Health Risks Scale, a measure of the perceived addictive potential and other health risks associated with cigarettes, e-cigarettes and nicotine gum
6. Tobacco Product Interest Scale, a visual analog scale assessing interest in use of various tobacco and nicotine products

In-Person Lab Visit 1

After completing Virtual Visit 1, participants will complete the COVID screener within 24 hours of their Lab visit via email or phone. Research staff will wear personal protective equipment including face masks and gloves. The participants will be required to wear facemasks when interacting with the staff. If participants do not have a mask, one will be provided to them to use for the remainder of the study. Temperature checks will be conducted immediately upon arrival using a thermal heat scanner.

Participants will provide carbon monoxide (CO) readings at least 6-feet away from other people, including the research staff, while they have their masks off. NicCheck Strips, which assess cotinine levels in urine, will also be used to confirm smoking status if participants have an expired breath CO reading less than or equal to 8 ppm. Participants with child-bearing potential will complete a urine pregnancy test. Participants will also be given the opportunity to sample the alternative tobacco and nicotine products that will be available during the ETM. Products include: fruit, dessert, mint, menthol, and tobacco flavored e-liquids; non-menthol preferred brand cigarettes; and mint, fruit and cinnamon flavored nicotine gum. Product sampling will occur at least 10-feet from other people, including the research staff. The sampling phase allows participants to draw upon personal experiences when completing the ETM task during Virtual Visits 2-5. This increases the study's validity by reducing the likelihood that they will purchase products from the ETM that they will not use during the field assessment and increases the likelihood of adherence to only using study products.

For the cigarettes and e-liquids, they will be instructed to take puffs ad lib for up to 2 minutes. For nicotine gum, they will be instructed to keep the product in their mouth for up to 2 minutes.

Virtual Visits 2-5

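### Field-week scale scores are compared between about 20 people per condition with no baseline adjustment specified, although pre-field readings on the same scales are already collected

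*Combined protocol and SAP*

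**What the plan says.** Under Virtual Visits 2-5, each participant receives field products from one of the four marketplace conditions, chosen at random: "In reality, we will randomly assign which condition is used 1, 2, 3, or 4". The same section gives the purpose of the measurements: "Actual product use enables us to measure their subjective experiences such as withdrawal, craving, or product satisfaction as well as assess changes in carbon monoxide". It then states the comparison: "We will conduct between-subjects analyses comparing these secondary outcomes by marketplace condition".

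The Exploratory Outcomes list names the scales in the form "Mean Minnesota Nicotine Withdrawal Scale scores", "Mean Questionnaire on Smoking Urges scores" and "Mean Product Evaluation Scale scores", with similar entries for perceived health risk, product interest and tobacco policy. No visit, change score or baseline adjustment is attached to any of them.

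The Statistical analysis plan section gives no model for these scales. Its mixed model concerns purchasing, lists three of the four conditions and relies on repeated measures of the same person. Its only pre/post test is also on purchasing.

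The visit schedule shows what is available:
- Withdrawal and urges: Virtual Visits 1, 2-5 and 6.
- Perceived risk, product interest and policy support: Virtual Visits 1 and 6.
- Product evaluation: the Cigarette Evaluation Scale at Virtual Visit 1 and the Product Evaluation Scale at Virtual Visit 6.

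Field products are first handed over at In-Person Lab Visit 2, after Virtual Visit 5.

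**The concern.** The main purchasing comparisons are within-participant and use all 80 people. The field-week comparison is between people, with roughly a quarter of the sample in each condition. People differ in how much withdrawal and craving they report and in what they believe about risk. In a between-person comparison those stable differences go into the error term unless a pre-field reading removes them. Here the readings exist and the plan does not say they will be used.

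Two things are at stake. One is precision in a comparison that is already small. The other is an open choice: Virtual Visit 6 alone, a change score and a baseline-adjusted score all fit the present wording, and they can give noticeably different standard errors.

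**Working it through.** **Plan's own figures.** The Power calculation section covers within-participant purchasing only. A paired t-test with n = 80, d = 0.31 and two-sided 0.05 has 78.2% power by the noncentral t (79.2% by the normal approximation), against the stated 80%; the exact detectable value is 0.317. The equivalence test with a margin of 0.33 SD and 0.05 per side gives 80.0%. Both reproduce to within two percentage points. Neither applies to the field week, for which no power is stated.

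**Inputs for the field week.**
- Completers: 80, from Subject Selection Criteria ("We anticipate recruiting up to 100 participants to achieve 80 completers").
- Conditions: 4. No ratio or blocking is stated, so an equal split is assumed: 80 / 4 = 20 per condition. Under simple randomisation a given condition would have 13 to 28 people (95% range).
- Two-sided 0.05, 80% power, no multiplicity correction (assumed).
- Correlation r between pre-field and Virtual Visit 6 scores: not in the documents, so a range is shown. When several pre-field visits are averaged, all visits are assumed equally correlated.

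**Unadjusted.** Normal approximation: (1.960 + 0.842) × √(2/20) = 0.886 SD. The two-sample noncentral t gives 0.909 SD. Power for a 0.5 SD difference is about 34%. The plan uses 0.5 for purchasing; it is only a yardstick here.

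**Using pre-field scores.** Multiply 0.909 by the square root of the variance factor:
- one pre-score as covariate: 1 − r²
- mean of four pre-scores (Virtual Visits 2-5) as covariate: 1 − 4r²/(1 + 3r)
- change from one pre-score: 2(1 − r)

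| r | One pre-score as covariate | Mean of four as covariate | Change score |
|---|---|---|---|
| 0.3 | 0.909 × 0.954 = 0.87 | 0.909 × 0.900 = 0.82 | 0.909 × 1.183 = 1.08 |
| 0.5 | 0.909 × 0.866 = 0.79 | 0.909 × 0.775 = 0.70 | 0.909 × 1.000 = 0.91 |
| 0.6 | 0.909 × 0.800 = 0.73 | 0.909 × 0.697 = 0.63 | 0.909 × 0.894 = 0.81 |
| 0.7 | 0.909 × 0.714 = 0.65 | 0.909 × 0.606 = 0.55 | 0.909 × 0.775 = 0.70 |

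Entries are detectable pairwise differences in SDs of the Virtual Visit 6 score. Pooling the error over all four conditions lowers each by about 1% (unadjusted 0.90). The change score is worse than no adjustment when r is below 0.5, and worse than the covariate at every r shown. With one pre-score, the covariate is worth an effective 20/0.75 = 26.7 people per condition at r = 0.5, or 20/0.51 = 39.2 at r = 0.7.

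**The case against.** The strongest reply is that nothing here is invalid. Assignment to field condition is random, so an unadjusted comparison is unbiased, and its standard error already reflects person-to-person differences. A reader might infer that chance imbalance between small groups will pass for an effect of the marketplace condition. That does not follow: such imbalance is covered by the nominal 5% error rate. Only precision is lost. This stands.

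Nor does the plan forbid adjustment; it is silent. Calling the outcomes raw scores would turn silence into a decision. This also stands.

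A reader might take the mean scores as averages over all six visits, which would dilute a field-week effect to one sixth. The text does not support that. The section Virtual Visits 2-5 ties these measures to actual product use, and Virtual Visit 6 is the only survey visit after use begins.

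The change from the Cigarette Evaluation Scale to the Product Evaluation Scale may look like an error. It is coherent: at Virtual Visit 1 participants have not yet sampled the study products, and no pre/post comparison of that scale is planned. The only consequence is that the Product Evaluation Scale has no baseline on the same instrument.

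Finally, the gain is limited. Even after adjustment the comparison detects only fairly large differences, and the plan claims no power for it. That is true, but it is no reason to leave out readings already collected.

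**Conclusion.** The point holds as a nearly free improvement in precision. With 20 per condition, the detectable pairwise difference falls from about 0.91 SD to 0.79-0.65 SD with one pre-score, or to 0.70-0.55 SD with the mean of Virtual Visits 2-5, for r between 0.5 and 0.7. These figures rest on an equal split, assumed correlations and no multiplicity correction; Bonferroni over six pairs would raise the unadjusted figure to 1.15 SD.

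Two limits on scope apply. The sentence on between-subjects analyses directly names withdrawal, craving, product satisfaction and carbon monoxide. Perceived risk, product interest and policy support come in through its open wording and the outcome list. Carbon monoxide is already described as a change, so the gap concerns the scales.

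A reader might also infer that validation of the purchasing task depends on these scales. The plan rests validation on real-world use of the purchased products and presents the scales as something that use also allows to be measured.

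Severity is minor. The outcome list places these scales under exploratory, and Aims 1 and 2 are unaffected. The conflict between that label and the word secondary in the section Virtual Visits 2-5 is real and should be resolved.

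**What to change.** Add a short paragraph to the statistical analysis plan:

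- The field outcome for each scale is the Virtual Visit 6 score, compared by randomly assigned field condition in a linear model with the participant's pre-field score as a covariate, not as a change score.
- The pre-field score is the mean of Virtual Visits 2-5 for withdrawal and urges, and the Virtual Visit 1 score for perceived risk, product interest and policy support.
- The Product Evaluation Scale is compared by assigned condition. The Cigarette Evaluation Scale may be a covariate but is not a pre-score. Any summaries by product used are descriptive only, because product use is a post-randomisation choice and grouping by it would break the randomised comparison.
- These outcomes carry one status, secondary or exploratory, in both places.

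The plan does not say when field condition is drawn or disclosed. It should confirm that participants do not learn it before the Virtual Visit 5 surveys, so that the covariate is truly pre-field.

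The cost is wording and one model degree of freedom per covariate (76 to 75 error degrees of freedom with 80 completers). No visit, questionnaire or participant is added.
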